### 13.8 Adverse Event Outcome Classification

Outcome of the event will be defined according to the following:

- *Resolved:* The event has fully resolved at the end of the study.
- *Resolved with sequelae:* The event has resolved, but retained pathological conditions resulting from the prior disease or injury.
- *Continuing:* The event is ongoing at the end of the study.
- *Death:* This event is determined to be the cause of death.

### 13.9 Device Deficiencies

A device deficiency is an inadequacy of a medical device related to its identity, quality, durability, reliability, safety, or performance, such as malfunction, misuse or use error and inadequate labeling.

All device deficiencies will be documented and the device should be returned to Motus GI for analysis, if possible. Instructions for returning the investigational device will be provided. Device deficiencies should also be documented in the subject's medical record.

Device deficiencies are NOT to be reported as AEs. However, if there is an AE that results from a device deficiency, that specific event would be recorded on the appropriate CRF.

### 13.10 Adverse Event Recording and Reporting

Assessment of the occurrence of an AE will be based on changes in the subject's signs and symptoms. AEs will be monitored until a subject completes the study unless the Investigator determines the event is related to the investigational device, in which case they will be monitored until resolution if possible. Medical care will be provided, as defined in the informed consent, for any AE related to study participation. AEs will be collected on an AE CRF and applicable source documentation.

The following should not be considered an AE:

Document title:	Document No.	Version	Page 36 of 61
Optimizing the Preparation Regime Prior to Colonoscopy Procedure with Pure-Vu System	CL00042	1.0	

- A condition requiring a preplanned procedure unless the condition worsened since screening
- A preexisting condition found as a result of screening, unless the condition has worsened since enrollment.

All AEs observed during the course of this study, regardless of severity or relationship to the investigational device will be recorded on the appropriate CRF.

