## 7.2 Anticipated Risks Associated with bowel preparation agents

The Bowel preparation agent used in this study are approved in U.S.

The main anticipated risks associated with the bowel preparation agents including nausea with or without vomiting, abdominal pain and dehydration.

The preparation in this study is less intensive compared to the standard preparation done prior to colonoscopy procedure, thus we expect that the risks related to the preparation agent will be similar or even lower than the risks following a standard preparation to colonoscopy procedure.

Reduction of the bowel preparation regimen will minimize patient discomfort and AEs associated with bowel cleansing, and potentially maximize the efficacy of the colonoscopy procedure with Pure-Vu System.

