## 10.0 Subject Selection and Enrollment

After being informed of the nature of the study, the subject will sign a written informed consent form (ICF) that has been approved by the appropriate IRB of the respective clinical site. Enrollment of up to 100 subjects is planned.

Subjects' participation in the study will last approximately 8 days, including the procedure day, five days prior for bowel preparation, and the follow up period.

Subjects will be considered for the study if they meet the specific inclusion/exclusion criteria. The criteria for enrollment must be followed explicitly.

Enrollment completion is expected to take place up to 12 months following IRB approval of the study.

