## 12.4 Effectiveness Analyses

### Safety Analysis

The secondary endpoint is to evaluate the Device related adverse event and the overall adverse events rate. The safety analysis set will consist of all patients who were enrolled into the study.

Individual listings of adverse events including type of device, adverse events (reported term), seriousness, duration, relationship to the study device, severity and the adverse events outcome will be provided for the total population and per study arm. AEs will be summarized using frequency counts and percentages per study arm.

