### 13.1 Adverse Event (AE)

An AE is any untoward medical occurrence, unintended disease or injury, or untoward clinical signs (including abnormal laboratory findings) in subjects, whether or not related to the investigational medical device.

This definition includes events related to the investigational medical device or the comparator and the procedures involved.

AEs will be collected starting from the time subject is enrolled until the follow-up period is completed.

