**Report Serious Adverse Event (SAE) within 48 hours of learning the event**

Adverse Event (AE) Form	Please Check
Have any AEs occurred during the study?	Yes / No
If yes,	
Start Date	__ / __ / __ DD MM YY
End Date	__ / __ / __ DD MM YY
Description:	
 
• Tissue trauma
 
• Excessive bleeding
 
• Laceration
 
• Other: _____
 
• Death
 

Severity	
 
• Mild
 
• Moderate
 
• Severe
 

Anticipated	Yes / No
Relation to the study	
 
• Unrelated
 
• Unlikely
 
• Possibly
 
• Related
 

Was the AE serious AE?	Yes / No
If yes, specify the reason	
 
• Death
 
• Life threatening
 
• Hospitalization
 
• Persistence / significant disability / incapacity
 
• Congenital anomaly / birth defect
 
• Important medical event (subject's health is at risk and intervention is required to prevent one of the above events) , specify
 

Document title:  Optimizing the Preparation Regime Prior to Colonoscopy Procedure with Pure-Vu System	Document No.  CL00042	Version  1.0	Page 61 of 61
---	-----------------------------	--------------------	------------------

	Date of Event report to the IRB:  ____ / ____ / ____ DD MM YY
Treatment?	Yes / No
If yes, specify type and reason	Pharmacological treatment  _____
	Other medical intervention  _____
Outcomes	

• Resolve

• Improved

• Unchanged

• Worsen

• Insufficient follow up

• Comments: _____

Investigator signature	_____
Date	____ / ____ / ____ DD MM YY

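### Section 13.10 follows an adverse event past study completion only if it is judged device-related, so events from the randomised bowel preparation, events from the colonoscopy alone, and serious events not judged device-related have censored duration and outcome

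*Protocol*

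**What the plan says.** Section 13.10 of the protocol sets the default and its single exception: "AEs will be monitored until a subject completes the study unless the Investigator determines the event is related to the investigational device". What then applies to such a device-related event is stated next: "in which case they will be monitored until resolution if possible". Section 13.1 closes collection at the same point: "AEs will be collected starting from the time subject is enrolled until the follow-up period is completed". Section 10.0 gives the length of the study for each subject: "participation in the study will last approximately 8 days, including the procedure day".

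The preparation has its own named risks in section 7.2: "The main anticipated risks associated with the bowel preparation agents including nausea with or without vomiting, abdominal pain and dehydration". Section 12.4 (Safety Analysis) plans individual listings that include duration, and says that "severity and the adverse events outcome will be provided for the total population and per study arm". Section 13.8 has a category, *Continuing*, for an unresolved event: "The event is ongoing at the end of the study". The adverse event form in Appendix F uses a different list of outcomes, one of which is "Insufficient follow up".

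**The concern.** The rule that decides which events are followed to their end depends on relation to Pure-Vu. Pure-Vu is common to both arms; the randomised factor is the magnesium citrate preparation. The study therefore follows through the events that its comparison is not about, and stops following those that could differ between arms. Section 5.1 names adverse event rates after the two preparations among the comparisons of interest, and section 9.2 lists adverse events as a secondary endpoint.

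Seriousness does not change the rule. If a patient is in hospital with dehydration attributed to the preparation when the call is made, 13.10 does not require the study to learn how that event ended. At stake is the completeness of the duration and outcome data by arm for the randomised exposure, and knowledge of how serious events ended.

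**Working it through.** This is a follow-up rule, so the check is a reading of the provisions plus a count of days.

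**1. Is there another exception?** The provisions that could supply one are:

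- 13.1 ends collection with the follow-up period.
- 13.2 to 13.5 define the serious and device-effect categories and set no follow-up.
- 13.8 codes an unresolved event as *Continuing* and sets no further contact.
- 13.11 sets reporting times and no follow-up to resolution.
- 13.10 promises medical care for events related to participation. That is care, not continued collection of data.

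None extends monitoring for a serious event, a preparation-related event or an event attributed to the colonoscopy alone.

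**2. When does the study end for a subject?** Section 10.0 gives about 8 days, including five days of preparation and the procedure day. The remainder is 8 − 5 − 1 = 2 days, which agrees with the 48-hour call in Appendix A and on the Appendix F form.

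The other wordings give a range:

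| Place | Timing of the last contact | Time after the procedure |
|---|---|---|
| Section 9.0 | 48 h ± 48 h | 48 − 48 = 0 h to 48 + 48 = 96 h |
| Section 11.1.5 | 2 working days | 2 days, or 2 + 2 = 4 across a weekend |
| Synopsis | 2 to 3 working days | 2 to 3 days, or up to 3 + 2 = 5 across a weekend |
| Appendix A, Appendix F | 48 h | 2 days |

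Under every wording, monitoring of an event not judged device-related stops within about 5 days of the procedure.

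**3. How long is a preparation event observed?** Appendix A places the preparation on days −1 to 0, and collection starts at enrolment. An event starting on day −1 is therefore seen for nominally 1 + 2 = 3 days, from onset to the call. One that settles within that time is fully captured. Only events still open at the call are affected.

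**4. What happens to the outputs in 12.4?** Counts and percentages per arm need only the occurrence of an event during the study, and all events observed are recorded whatever their severity or relationship. They do not change. Duration is right-censored at the call for an open event, and outcome is recorded as it stood then. For a device-related event, both can be completed later.

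**5. Do the outcome lists agree?** Section 13.8 has *Resolved*, *Resolved with sequelae*, *Continuing* and *Death*. The Appendix F form has *Resolve*, *Improved*, *Unchanged*, *Worsen* and *Insufficient follow up*, with a comments line. *Resolved with sequelae* and *Death* are not outcome options on the form. The three middle options can express an ongoing event.

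**The case against.** Several points on the other side stand and limit the conclusion.

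- A reader might infer that patients with open events are abandoned. The document does not support that: 13.10 promises care for events related to participation and has all observed events recorded. What ends is the study's monitoring.
- A reader might infer a bias between arms in adverse events. The rule is the same in both arms, and the only planned adverse event summary, counts and percentages, does not depend on follow-up after the call.
- The promise in 12.4 is formally kept. Section 13.8 defines outcome as of the end of the study, so an open event has a valid code. The loss is of information.
- The oversleeve is mounted on the colonoscope, section 13.3 defines a device effect broadly, and 13.7 allows possible and probable relationships. Some bleeding or perforation may be judged device-related and so be followed to resolution. The preparation events are the firmer ground.
- A reader might infer that the form cannot record an ongoing or fatal event. It can: *Improved*, *Unchanged* and *Worsen* describe ongoing events, and death appears both as a description and as a reason for seriousness. Only a mismatch of labels with 13.8 remains.
- The consent form is not available and might contain a longer commitment. Nothing in the protocol as shown does.

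None of this supplies follow-up for a preparation-related or serious event that is open at the call and not judged device-related.

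**Conclusion.** The point holds as a cheap and worthwhile improvement to safety follow-up. It is not an error that invalidates an analysis. The trigger in 13.10 is tied to the exposure shared by both arms and omits the randomised one, and it makes no allowance for seriousness. The consequence is censored duration and a provisional outcome, in the listings by arm, for events still open at a call made 0 to 96 hours or 2 to 3 working days after the procedure.

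The protocol gives no rate for such events, so the number affected, among at most 100 subjects, cannot be stated. The primary endpoint and the adverse event counts per arm are untouched. The conclusion assumes that sites apply 13.10 as written and that no document outside the protocol requires longer follow-up. An analysis plan could not repair this, because the outcomes would not have been collected.

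**What to change.** In 13.10, widen the condition for follow-up to resolution, for example: *Events judged related to the investigational device, the bowel preparation or the colonoscopy procedure, and all serious events whatever their relationship, are monitored until resolution where possible.* Reconcile the timing of the follow-up call across the synopsis, section 9.0, section 11.1.5, Appendix A and Appendix F, so that the end of ordinary monitoring is the same everywhere.

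As a minor alignment, give the Appendix F form the four outcome categories of 13.8, plus one for unknown or lost to follow-up.

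The cost is one sentence in 13.10, one field on the form, and a few extra contacts for events still open at the call. The reconciliation of the call timing is editorial.

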### **13.11 Reporting Responsibilities**

An investigator shall submit to the sponsor and to the reviewing IRB a report of any unanticipated SAEs, ADEs, SADEs, USADEs, and device deficiencies that could have led to a serious adverse device effect occurring during an investigation within 24 hours of learning of the event, but in no event later than 10 working days after the investigator first learns of the effect.

A sponsor who conducts an evaluation of an unanticipated adverse device effect under 812.46(b) shall report the results of such evaluation to FDA and to all reviewing IRB's and participating investigators within 10 working days after the sponsor first receives notice of the effect.

Thereafter the sponsor shall submit such additional reports concerning the effect as FDA requests (21 CFR Part 812.150).

## **14.0 Ethics and Compliance**

### **14.1 Statement of Compliance**

This clinical investigation will be conducted in accordance with the ethical principles that have their origin in the Declaration of Helsinki, ISO 14155:2011 (Clinical Investigation of Medical Devices for Human Subjects – Good Clinical Practice), ICH-GCP, and any regional or national regulations, as appropriate.

This may include an inspection by Motus GI representatives and/or Regulatory Authority representatives at any time. The investigator must agree to the inspection of study-related records by the Regulatory Authority/ Motus GI representatives, and must allow direct access to source documents to the Regulatory Authority/ Motus GI representatives. Regulatory Authority approvals/authorizations/notifications, where required, will also be in place and fully documented prior to study start.

Document title:	Document No.	Version	Page 37 of 61
Optimizing the Preparation Regime Prior to Colonoscopy Procedure with Pure-Vu System	CL00042	1.0	

## 14.2 Protocol Compliance

No changes to the protocol will be permitted without the written approval from Motus GI and the IRB. The investigator must notify Motus GI and the reviewing IRB of any deviation from the Investigational Plan when specific to the protection of the life or physical well-being of a subject in an emergency. Such notice must be given as soon as possible, but in no event later than 5 working days after the emergency has occurred. Except in such an emergency, prior written approval by Motus GI is required for changes in or deviations from the Plan. If these changes or deviations affect the scientific soundness of the Plan or the rights, safety, or welfare of human subjects the IRB will also be notified. All other deviations will be reported per the site's IRB deviation policy. Should any deviations from the Investigational Plan occur, these will be reviewed by Motus GI for their clinical significance. If the event is performed without written approval from all parties, the investigator may be terminated from the study.

## 14.3 Institutional Review Board (IRB)

Documented approval from the appropriate Institutional Review Board (IRB) will be obtained for all participating centers prior to study start, according to ICH GCP, local laws, regulations, and organization. When necessary, an extension, amendment, or renewal of the IRB approval must be obtained. The IRB must supply to the sponsor a list of the IRB membership and a statement to confirm that the IRB is organized and operates according to GCP and applicable laws and regulations.

## 14.4 Subject Informed Consent

A core information and consent form will be provided. Prior to the beginning of the trial, the investigator must have the IRB written approval/favorable opinion of the written ICF and any other written information to be provided to subjects. The written approval of the IRB together with the approved subject information/ICFs must be filed in the study files.

The process of obtaining informed consent must be in accordance with applicable regulatory requirement(s), and must adhere to GCP and to the ethical principles originating in the Declaration of Helsinki. Written informed consent must be obtained before any study specific procedure takes place. Participation in the trial and date of informed consent given by the subject should be documented appropriately in the subject files.

Document title:  Optimizing the Preparation Regime Prior to Colonoscopy Procedure with Pure-Vu System	Document No.  CL00042	Version  1.0	Page 38 of 61
---	------------------------------------	---------------------------	------------------

## 14.5 Insurance

All subjects participating in the trial will have insurance coverage by the Sponsor, which is in line with applicable local laws.

## 14.6 Confidentiality

All records identifying the subject will be kept confidential and, to the extent permitted by the applicable laws and/or regulations, will not be made publicly available.

Subject names will be kept confidential. Only the subject number and initials will be recorded in the CRF, and if the subject name appears on any other document, it must be obliterated. In cases where the local law does not allow using the subject initials serial number will be appointed (e.g. AAA, BBB). Study findings stored on a computer will be stored in accordance with local data protection laws. The subjects will be informed in writing that representatives of the sponsor, IRB or Regulatory Authorities may inspect their medical records to verify the information collected, and that all personal information made available for inspection will be handled in strictest confidence and in accordance with local data protection laws. Subjects will also be informed that information regarding the study that does not include subject identifiers will be posted on clinicaltrials.gov.

If the results of the trial are published, the subject's identity will remain confidential.

The investigator will maintain a list to enable subjects' records to be identified.

## 14.7 Use of Data and Publications

Information regarding the study and study data will be made available via publication on clintrials.gov.

All data and results and all intellectual property rights in the data and results derived from the study will be the property of Motus GI, who may utilize the data in various ways, such as for submission to government regulatory authorities or disclosure to other investigators, educational, further product development and marketing uses.

The investigator, while free to utilize data derived from the study for scientific purposes, must discuss any publication with the sponsor prior to release and obtain written consent of the sponsor on the intended publication. The sponsor recognizes the right of the investigator to publish the results upon completion of the study. However, the investigator must send a draft CL00042/ Protocol, Version 1.0 December 13, 17

Document title:	Document No.	Version	Page 39 of 61
Optimizing the Preparation Regime Prior to Colonoscopy Procedure with Pure-Vu System	CL00042	1.0	

manuscript of the publication or abstract to the sponsor 45 days in advance of submission in order to obtain approval prior to submission of the final version for publication. This will be reviewed promptly and approval will not be withheld unreasonably. In case of a difference of opinion between the sponsor and the investigator(s), the contents of the publication will be discussed in order to find a solution which satisfies both parties.

Disclosure of involvement in a publication (e.g., sponsor of the study; collection, analysis, and interpretation of data; professional writing assistance) must be as specified by journal-specific policies, submission requirements, and prevailing editorial standards, in addition to those specified by International Committee of Medical Journal Editors. Authors must ensure that an acknowledgement/disclosure statement is included in the body of the manuscript for Motus GI to review for accuracy. All authors must also disclose financial or personal affiliations that could be considered conflicts of interest as per journal requirements.

## 15.0 Monitoring Procedures

Site visits will be conducted by an authorized Motus GI representative to inspect study data, subjects' medical records, and CRFs in accordance with current ICH GCPs and the respective local and national government regulations and guidelines (if applicable). The Study Investigator and the investigating site will permit authorized clinical research personnel and clinical monitors from Motus GI and/or designee(s) employed by Motus GI to review completed CRFs, IRB decisions, and Investigator, clinical site records, and facilities relevant to this study at regular intervals throughout the study per the monitoring plan. Additionally, subject charts and clinical records will be requested and reviewed so that protocol adherence and source documentation can be verified. The accuracy and quality of the data obtained from the investigator and maintained by Motus GI will be confirmed through a structured program of clinical field auditing and internal review detailed in the monitoring plan. In instances where data protection regulations prohibit the direct examination of hospital records by the study Sponsor or designee(s), the Investigator will cooperate in a system of source data verification with the Sponsor. Monitoring may be performed with in person visits or remotely, when applicable.

To ensure the rights, safety, and welfare of study subjects are being maintained, the monitor will review training records to ensure all study staff are trained on the study protocol and use of the study devices. If the monitor discovers that an investigator is not complying with the signed Investigator Agreement, the investigational plan, applicable laws, or any conditions of approval

Document title:	Document No.	Version	Page 40 of 61
Optimizing the Preparation Regime Prior to Colonoscopy Procedure with Pure-Vu System	CL00042	1.0	

imposed by the reviewing IRB, the monitor will report to the Sponsor and take such steps necessary to promptly secure compliance. If compliance cannot be secured, device shipments to the investigator may be discontinued and the investigator's participation in the investigation terminated. The monitor shall also require such an investigator to dispose of or return the device, unless this action would jeopardize the rights, safety, or welfare of a subject.

